The trial will be conducted in accordance with International Council on Harmonisation Good Clinical Practice (ICH GCP) and applicable United States (US) Code of Federal Regulations (CFR); specifically the United States (US) Code of Federal Regulations (CFR) applicable to clinical studies (45 CFR Part 46, 21 CFR Part 50, 21 CFR Part 56, 21 CFR Part 312, and/or 21 CFR Part 812). The Principal Investigator will assure that no deviation from, or changes to the protocol will take place without prior documented approval from the Institutional Review Board (IRB), and the Investigational Device Exemption (IDE) sponsor, if applicable, except where necessary to eliminate an immediate hazard(s) to the trial participants. All personnel involved in the conduct of this study have completed Human Subjects Protection and ICH GCP Training.

The protocol, informed consent form(s), recruitment materials, and all participant materials will be submitted to the IRB for review and approval. Approval of both the protocol and the consent form(s) must be obtained before any participant is consented. Any amendment to the protocol will require review and approval by the IRB before the changes are implemented to the study. All changes to the consent form(s) will be IRB approved; a determination will be made regarding whether a new consent needs to be obtained from participants who provided consent, using a previously approved consent form.

Investigator's Signature

The signature below constitutes the approval of this protocol and provides the necessary assurances that this study will be conducted according to all stipulations of the protocol, including all statements regarding confidentiality, and according to local legal and regulatory requirements and applicable US federal regulations and ICH guidelines, as described in the *Statement of Compliance* above.

Email: [contact]

[contact]

PROTOCOL SUMMARY

Synopsis 1.1

Title: Retrospective Study on the Use, Efficiency and Safety of

the at-home insemination Mosie Kit

Study Description: This study examines the experience of people who have

> selected to use the at-home insemination Mosie Kit to understand the user's experience, the perceived safety and the efficiency. People who have recently purchased and voluntarily selected to use the Mosie Kit will be invited to complete a one-time online anonymous survey. The results

of the survey will be analyzed to understand their

experiences.

The primary objective is to understand how many people end up pregnant by using the at-home insemination Mosie

Kit during up to 6 cycles of voluntary use and how many people get pregnant using the Mosie Kit without using sex because they are either single, in a same-sex relationship, or in an unconsumated mariage due to infertility problems. The secondary objectives are to understand perceived safety and ease of use of the at-home Mosie Kit.The

tertiary objective will be to examine pregnancy outcome in relationship to self-reported reason for infertility. Additionally, since COVID-19 has recently affected

everyone, its effect on family expansion plans and stress

will also be examined.

Endpoints*: The specific study endpoints include pregnancy rates after

up to 6 cycles of at-home intracervical insemination (ICI),

perceived ease of use, perceived safety, and the

relationship of infertility source with pregnancy outcome rates, stress related to COVID-19 and its impact on family

expansion plans.

Study Population: The sample will be drawn from all people who have

purchased an at-home Mosie Kit in the past 2-8 full months

prior to the study commencement. The approximate

sample size will be 500 but all will be invited to participate.

Objectives:

MOSIE-001

Both females and males will be included in the study. It is expected that the age range of the participants will vary from approximately 21 - 50 years of age. The participants will have a history of fertility problems, specifically problems getting pregnant. Otherwise, the participants should be in overall good health. No other health conditions are being used as exclusion criteria for participation in the study. Participants may be located anywhere in the world as this study will be conducted using an online web-based survey.

Phase or Stage:

This is a post-market retrospective study to examine the experience people have with using the Mosie Kit for at-home insemination.

Description of Sites/Facilities Enrolling Participants:

No sites or facilities will be used in this study. Participants will be existing Mosie Baby Clients who have purchased a Mosie Kit in the prior 8 months. Participants may reside anywhere in the world.

Description of Study Intervention/Experimenta I Manipulation: This is a retrospective study. Participants completing the study survey will have voluntarily purchased a Mosie Kit in the prior 8 months. Each participant will be asked to complete one study survey. Each participant will receive up to 5 email invitations to participate in the study. The study survey will be administered anonymously online on an individual basis.

tion .

Study Duration:

It is estimated that participants will complete the retrospective study survey within one month of receipt of the initial email requesting their participation. However, the study might continue until sufficient surveys are collected.

Participant Duration:

Participants will be able to complete all study related questions in less than 25 minutes (approximately 10-20 minutes).

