3 OBJECTIVES AND ENDPOINTS

OBJECTIVES	ENDPOINTS	JUSTIFICATION FOR ENDPOINTS	PUTATIVE MECHANISMS OF ACTION
Primary			
The primary objective is to understand the outcome of using the at-home intracervical insemination Mosie kit, i.e. pregnancy rate after its use.	The primary endpoints is: Pregnancy Rate after up to 6 cycles. Another primary end point is to understand the rates of pregnancy in people who desire to get pregnant without intercourse (i.e. both single and those in LGBTQ relationships.	The ultimate objective of using the Mosie Kit is to end up pregnant. Thus pregnancy rate is a primary endpoint. Specifically, pregnancy rate in up to 6 (six) cycles will be examined as it is the typical standard timeframe for attempting to get pregnant using IVI or IUI before seeking an alternative method. People who have no known fertility issue who are trying to conceive without intercourse such as those who are in LGBTQ relationships or those who are not in any relationship at all will likely have higher pregnancy rates than those with known fertility issues of female origin. Women in LGBTQ relationships wishing to conceive might also have a higher pregnancy rate than those in heterosexual relationships where infertility might be caused by things like low sperm count, sperm motility issues or erectile dysfunction (ED).	The Mosie Kit is intended to be used to deposit semen at or near the cervix where the sperm will have an increased likelihood of entering the uterus and pairing up with the ovum resulting in a pregnancy. Pregnancy rates increase when sperm reaches the ovum and fertilizes it. In people with no known fertility issues, the Mosie kit deposits the semen where it is able to fertilize the ovum. People without infertility issues who want to get pregnant without sex by using the Mosie Baby are also more likely than people with known fertility issues to get pregnant.

Secondary			

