5.1 Inclusion Criteria

In order to be included in the study, the following inclusion criteria will be used.

Inclusion Criteria:

- Provide implicit consent by filling out and submitting the survey.
- Used a Mosie Kit to conceive during at least one cycle.
- At least 18 years old.
- Has an active email on file (presumed or they would not have received an invitation to participate. This information will not be verified as there is a desire to keep the survey completely anonymous.)

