5.2 Exclusion Criteria

The following exclusion criteria will be used.

Never used a Mosie Kit

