6.5 Concomitant Therapy

N/A

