9.4.3 Exploratory Analyses

Additional exploratory data analysis will be conducted to examine the main characteristics of the data. This analysis will be done using descriptive statistics, scatter plots, and odds ratio. If the exploratory analysis warrants the testing of new hypotheses, t-test or ANOVA may be used for further analysis.

Exploratory modeling will be conducted to examine multiple variables and their relationship to the pregnancy outcome. This will include the source of infertility, age, number of inseminations, number of cycles, lying time, and type of relationship. The model will use correlations and goodness of fit tests in its analysis.

1 0 SUPPORTING DOCUMENTATION AND OPERATIONAL CONSIDERATIONS

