[figure not shown]
How did you or your partner time your ovulation? (Select all that apply.) *
Count days in cycle
Track vaginal or cervical fluids
Tracking changes in the cervix
Use ovulation predictor kit
Use an app to estimate ovulation
Basal Body Temperature
Wearable device
Did not time ovulation
Did using Mosie result in a pregnancy? *
O Yes
O No
Back Next Page 10 of 20

[figure not shown]
Never submit passwords through Google Forms.

 $This \ content \ is \ neither \ created \ nor \ endorsed \ by \ Google. \ \underline{Report \ Abuse} - \underline{Terms \ of \ Service} - \underline{Privacy \ Policy}$

Google Forms

Page 56

[figure not shown]

Safe process

Enjoyable

	Very Easy	Easy	Neutral	Difficult	Very Difficult
To collect the semen/sperm sample in the cup?	0	0	0	0	0
To draw up the semen/sperm in the syringe?	0	0	0	0	0
Insert the Mosie syringe into the vagina up to the handles?	0	0	0	0	0
To deposit the semen/sperm at or near the cervix using the syringe?	0	0	0	0	0
My overall impression on the ease of use	0	0	0	0	0
					Page 12 of 20
submit passwords to	through Google Fo				

MOSIE-001 © 2020 Mosie Baby Page 59

MOSIE-001 © 2020 Mosie Baby

Page 60

Pulled the syringe plunger back and forth to confirm it was functioning.

My partner washed their hands

Use a sperm friendly-lubricant.

Thawed out donor sperm from sperm bank

Prepared all items and have them handy ready to use.

Washed the penis

that	apply)?*
	Lie down in a comfortable position.
	Relax
	Receive oral sex
	Stimulate clitoris
	Use any vibratory or non-vibratory stimulation device intravaginally
	Have an orgasm
	Other:
	erall, how well were you able to use the Mosie syringe to inseminate yourself our partner? * Very Able
	our partner? *
or y O O O	our partner? * Very Able Able Not Very Able
or y 0 0 0 0	Very Able Able Not Very Able Not Able at All Volume at All Volume at All Volume at All Volume at All Able at All Volume at All Able at All Able at All
or y O O O	Very Able Able Not Very Able Not Able at All Volong did you remain laying down after using the Mosie syringe? * Less than 15 minutes

Willelf best descri	ibes your lying position? *	
On my stomach	n	
On my side		
On my back		
On my back wit	th my hips elevated by a pillow	
Other:		
O No		
O		
What type of sam	ple did you use? *	
What type of sam	ople did you use? * rom a sperm bank (frozen)	
What type of sam	rom a sperm bank (frozen)	

0 2000	thank 50%	
O 51%-	70%	
O 71% -	80%	
O 81%-	90%	
O 90%-	95%	
O 96%-	100%	

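### The plan has no rule for separating kit-only pregnancies from those in cycles that also involved intercourse or another method, and it reaches the no-intercourse objective only through relationship type

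*Combined protocol and SAP*

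**What the plan says.** The second primary objective in the Synopsis (section 1.1) is "how many people get pregnant using the Mosie Kit without using sex", and it names three groups: single people, same-sex couples and unconsummated marriages. Section 3 words the matching endpoint more narrowly, as rates in "people who desire to get pregnant without intercourse (i.e. both single and those in LGBTQ relationships"; unconsummated marriage is not listed there.

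Eligibility depends only on use of the kit. Section 5.1 requires "Used a Mosie Kit to conceive during at least one cycle", and the one exclusion in section 5.2 is "Never used a Mosie Kit". Neither sets a condition on other methods. The entry under "6.5 Concomitant Therapy" is N/A.

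The outcome item visible in Appendix A is "Did using Mosie result in a pregnancy", answered yes or no. Appendix A also shows a list of other methods: intercourse, another syringe, IUI, Femara, Clomid, IVF and cervical cap. The question above that list is in a figure that is not reproduced, so its time frame is unknown.

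Under section 9.1, Primary Hypothesis 1 sets the total pregnancy rate against a 10-20% IUI rate. For Primary Hypothesis 2, rates are described in six groups (LGBTQ, heterosexual and single, each with and without a known fertility issue). The three groups with an issue are then pooled against the three without. Section 9.4.1 summarises every survey item descriptively. Section 9.4.2 lists subgroups and does not include concurrent methods. Of the exploratory model, section 9.4.3 says: "This will include the source of infertility, age, number of inseminations, number of cycles, lying time, and type of relationship".

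**The concern.** A respondent who used the kit and also had intercourse, or had IUI or an ovulation drug in the same cycle, cannot know which of them led to conception. The outcome item asks for that attribution and gives no rule for making it. The plan then pools the answers into one rate and compares it with an external benchmark. Background conceptions can therefore be counted in the kit's favour, and nothing pre-specified would show how many.

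The exposure is also uneven. Heterosexual couples can conceive in the background; single and LGBTQ users mostly cannot. The no-intercourse objective would give the cleanest view of the kit, but its groups are defined by relationship type and not by whether intercourse took place. Couples in unconsummated marriages fall among heterosexual users, alongside couples who do have intercourse.

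Section 2.3.2 says the results should help users weigh the kit against IUI, and section 10.1.3 allows aggregate results in marketing. The survey is anonymous with no follow-up (section 4.3), so an answer not collected at the time cannot be recovered.

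**Working it through.** **1. The plan's own figure.** Section 9.2 gives a 95% interval of ±4.4% at 500 surveys and ±5% at 384. Half-width = 1.96 × √(0.25/n): n = 500 gives 4.38 points and n = 384 gives 5.00 points. Both reproduce. The issue is what the rate measures, not its stated precision.

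**2. Inputs the documents do not give.** These are the background chance of conception per cycle without the kit (b), the share of respondents exposed to it (s), and the number of kit cycles (c). I assume b = 2-5%, s = 30-90% and c = 3 or 6. I also assume that exposure lasts for all c cycles and that every background pregnancy is reported as a kit pregnancy.

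**3. Background conception among exposed users, 1 − (1 − b)^c.**

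| b | 3 cycles | 6 cycles |
|---|---|---|
| 2% | 5.9% | 11.4% |
| 3% | 8.7% | 16.7% |
| 5% | 14.3% | 26.5% |

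**4. Pooled rate if the kit adds nothing, s × [1 − (1 − b)^c], for b = 2% to 5%.**

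| Share exposed | 3 cycles | 6 cycles |
|---|---|---|
| 30% | 1.8-4.3% | 3.4-7.9% |
| 60% | 3.5-8.6% | 6.8-15.9% |
| 90% | 5.3-12.8% | 10.3-23.8% |

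For example, 0.60 × 11.4% = 6.8% and 0.60 × 26.5% = 15.9%.

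**5. Pooled rate if the kit alone gives k = 10%.** The rate is k + s(1 − k)B, where B is the six-cycle figure from step 3. With s = 60%, b = 2% gives 0.10 + 0.60 × 0.90 × 0.114 = 16.2%, and b = 5% gives 24.3%. The background adds 6.2 to 14.3 points.

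**6. Effect on a test.** Section 9.1 names no test for Primary Hypothesis 1. As an illustration I use an exact one-sided binomial test at 0.05 with 500 respondents, in line with the one-tailed rule in section 9.4.1. Significance needs 62 pregnancies (12.4%) against 10%, or 116 (23.2%) against 20%. With a kit that adds nothing:

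- Six cycles, s = 60%, b = 3%: 5% chance of significance against 10%.
- Six cycles, s = 60%, b = 5%: 99% against 10%.
- Six cycles, s = 90%, b = 3%: 96% against 10%.
- Six cycles, s = 90%, b = 5%: 65% against 20%; near 0 against 20% in every other scenario run.
- Three cycles: 64% against 10% at s = 90%, b = 5%; near 0 in the other scenarios run.
- s = 30%: near 0 throughout.

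**7. Direction for Primary Hypothesis 2.** The hypothesis as stated sets LGBTQ and single users without an issue against heterosexual users with one. Background conceptions would raise the heterosexual comparator and work against the hypothesis. The planned pooled contrast has heterosexual users on both sides, so the net direction is undetermined.

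**8. Precision of a restricted set.** If 10-50% of 500 respondents qualify (assumed), n = 50 gives ±13.9 points and n = 250 gives ±6.2 points.

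**The case against.** Several objections have force. Each rules out a stronger reading that a reader might infer.

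- **That every such pregnancy is credited to the kit.** The documents do not show this. A respondent who believes she conceived another way can answer no. The list of other methods sits between the infertility-diagnosis item and the pregnancy history, so it may concern past attempts. Several survey pages are not reproduced, and a same-cycle question may exist.
- **That the list of other methods is never used.** Section 9.4.1 covers every survey question descriptively. Section 9.1 adds exploratory work on what else people do when using the kit, and the covariate list in section 9.4.3 need not be exhaustive. What is missing is a pre-specified use in the primary analyses.
- **That the no-intercourse objective goes unanswered.** Rates are planned for single and LGBTQ users, which meets the endpoint as section 3 words it, by proxy. Tertiary Hypothesis 2 partly reaches unconsummated marriages through vaginismus, erectile dysfunction and performance issues.
- **That background conception alone gives 11.4-26.5%.** This needs every respondent exposed for six cycles at an assumed rate. Single and LGBTQ users mostly are not exposed, and first-time buyers of two months ago cannot have six cycles.

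The N/A for concomitant therapy is weak evidence in a study with no intervention that sets out to observe natural use. A restricted set would also lean towards single and LGBTQ users, whom section 3 expects to do better if they have no fertility issue, so it changes the population as well as removing background conceptions.

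None of this supplies a rule for concurrent methods in the Primary Hypothesis 1 rate, or a group for unconsummated marriages.

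**Conclusion.** The concern holds as a gap in pre-specification. The rate compared with 10-20% is a total, self-attributed rate, and no primary, subgroup or listed model analysis separates kit-only cycles from cycles with intercourse, IUI, ovulation drugs or another method. The no-intercourse objective is addressed descriptively, by relationship type, without the unconsummated-marriage group that the Synopsis names.

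The size of the bias is unknown. Under the assumptions above, with 60% exposed and a kit that adds nothing, it is 3.5-8.6 points over three cycles and 6.8-15.9 points over six. It could decide the comparison with 10% when exposure is common and lasts six cycles. It is unlikely to matter when exposure is limited or there are few cycles. For Primary Hypothesis 2 the documents support no claim about direction.

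This is an inexpensive improvement worth making before the survey opens. It does not show that the result will be wrong.

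**What to change.** 1. Check that the survey asks, for the cycles in which the kit was used and for the conception cycle, whether intercourse or another method was also used. If it does not, add one item; Appendix A leaves room to revise questions.
2. Define the no-intercourse set by reported absence of intercourse and other methods in those cycles, including unconsummated marriages. Report its pregnancy rate with a 95% confidence interval.
3. Report Primary Hypothesis 1 in all users and in that restricted set. Break both down by relationship type and fertility status, so that a difference in case mix is not read as an effect of removing other methods.
4. Add concurrent method to the section 9.4.3 model.

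The cost is at most one survey item, one restricted analysis and one covariate. The restricted rate will be less precise: about ±6 to ±14 points for 250 down to 50 users (assumed), against ±4.4 for the full 500.

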1.2 Schema

Following is the flow of this study.

[figure not shown]
Total N: approximately 500. (approximately 4000 invitation emails) Identify all potential participants by obtaining a list of all people who have purchased a Mosie Baby Kit in the 2-8 full months prior to the initiation of the study. No other inclusion/exclusion criteria applies at this point.

Send all participants an initial email requesting their participation in the study. Up to an additional 4 reminder emails will be sent to encourage participation.

TIME POINT 1: Online survey completion.

1.3 Schedule of Activities

This study consists of completion of a one-time online survey. The following type of information is contained within this one-time survey:

- Informed consent
- Demographics (includes gender, sexual identification, type of relationship. race, ethnicity, household income and age. No identifying information will be requested)
- Fertility history and diagnosis if any
- Mosie Kit use and experience
- Post-Mosie Kit use pregnancy success rate
- Perceived safety
- Perceived ease of use
- Effect of COVID-19 on family expansion plans
- Effect of COVID-19 on stress

2 INTRODUCTION

2.1 Study Rationale

At-home intracervical insemination (ICI), folklorickly known as the "turkey-baster" method, has been used for decades to increase likelihood of pregnancy. This method works by depositing semen close to or at the cervix. While there are several devices such as over the counter syringes and silicone caps, the creator of the Mosie Baby syringe believes it is designed to be more ergonomic and compatible with a woman's body, easy and safe to use, and results in depositing the semen at or near the cervix opening. The Mosie Kit provides people with an at-home intracervical insemination option which could be used before resorting to more invasive and expensive options such as Intrauterine Insemination (IUI) or in vitro fertilization. There is vast evidence of Mosie's success in the form of happy users who have conceived. There is a desire to learn more about the safety, useability and experience of using the Mosie kit.

This retrospective study will examine the experience of people who have voluntarily chosen to purchase and use the Mosie Kit. The Mosie Kit consists of 2 syringes and a semen collection cup Understanding the safety, useability and experience of using the Mosie Kit will provide additional information about the nature of using intracervical insemination as a viable method for getting pregnant. The information gained will increase understanding of how viable the Mosie Kit is as a first step in trying to conceive and how it is perceived by the people who have chosen to use it.

2.2 Background

Infertility is defined as not being able to get pregnant after one year of unprotected sex. About 6% of married and overall 12% of women ages 15 to 44 have infertility issues. Infertility issues can be of male or female origin. According to the CDC, in 35% of the infertility cases a male factor was found along with a female factor and in 8% of the cases the only identifiable cause was a male factor. Fertility is affected by multiple factors, one of which is the female's age. For this reason it is recommended that people anatomically female under the age of 35 seek help after one year of trying to conceive while those over the age of 35 should seek help after 6 months. One of the first options available is artificial insemination.

The first documented case of artificial insemination was done in the 1770s by John Hunger in London (Obmelet & Robays 2015). Subsequently J. Mario Sims reported his findings in the mid-1880s. Sims describes 55 inseminations. Unfortunately since he believed ovulation occurred during meneses, only one pregnancy was reported (Obmelet & Robays 2015). Research has come a long way since the early 18th century. Artificial insemination is now a much more frequent occurrence. Initially used by couples with male infertility (low sperm count and inherited Y-chromosome disease), later for couples with physiological and psychological dysfunction, such as retrograde ejaculation, vaginismus, hypospadias and impotence, and now

is very commonly used by people with no male partner (both single and those in lesbian relationships).

Since [name] sperm freezing success in 1953 with a subsequent live birth, collecting and using sperm for insemination in humans was made possible. However, it would be more than a decade before it became legally possible as it was initially ruled as contrary to public policy and good morals. In the 1960s and 70s, sperm selection and washing techniques led to Intrauterine insemination (IUI) which placed the sperm even further into the woman's body by putting it directly into the uterus. By the 1970s sperm banks in the US became popular. Also in the 1970s, Steptoe and Edwards introduced the world to In-Vitro Fertilization (IVF). More recently, techniques such as intratubal insemination, and intraperitoneal insemination have been added to the available conception methods. During the last decades the popularity of Intrauterine Insemination (IUI) increased because it was safer, painless, and more cost-effective. Additionally, more information has become available about sperm selection techniques and now there is a greater understanding of many of the causes of infertility.

The most popular method of insemination is to use the husband's sperm (Artificial Insemination by Homologous or Husband (AIH)). In some cases anonymous donor sperm is used. Intracervical (ICI) or intravaginal insemination (IVI) are terms used interchangeably to describe the insemination technique colloquially known as the "turkey baster method". This method consists of placing the semen into the vagina at or near the cervix. In the United States, IUI is the most frequently doctor assisted technique. Some researchers have examined the success rates of each technique. ICI/IVI has been found to have a per cycle pregnancy rate of 10-15% while IUI has been found to be slightly higher up to 10-35%. Meanwhile techniques such as IVF can be as high as 31% in people under 35 years of age and as low as 3% for those above 43 according to the CDC.

Getting pregnant using IUI can cost \$250-500 per insemination before accounting for the cost of the testing and other imaging done as part of the process. IVF is even more expensive and invasive. According to Katz et al. 2011, the median per-person cost of IVF was approximately \$24,373 (for just IVF) to \$38,015 (for IVF-donor egg). Voorhis et al. 1997 found ICI to cost \$7.800-10,300 while Assisted Reproductive Therapy (ART) cost \$37,00 - 76,000. The cost difference between IVI/ICI, IUI and ART therapies such as IVF is significant. This makes cost a consideration for people attempting to conceive.

The good news is a number of studies such as Cohlen and Ombelet 2014 and Banerjee and Singla 2017, demonstrate the viability of using IVI/ICI as a means of AIH. The benefits of ICI is that it can be done in the privacy of the home, is relatively low cost, and over a 6 cycle time frame seems to have comparable rates to its more expensive counterparts.

Cohlen and Ombelet 2014 showed that for many couples with cervical factor infertility, psychological sexual dysfunction, physiological dysfunction, unexplained infertility and mild to moderate male subfertility using artificial insemination with a husband's sperm (AIH) was a

preferred treatment option. Banerjee and Singla (2017), tested couples with unconsummated marriages due to vaginismus, erectile dysfunction and premature ejaculation. They found 69% of couples ages 20-32, 43% ages 33-36, and 25% over 36 years old conceived using IVI. This is comparable to the expected 10-35% pregnancy rate of IUI.

Additionally, Kop et al. 2018 conducted a literature review to determine if there was a difference between pregnancy rates and live births of IUI versus ICI. They reported that out of six trials totalling 708 women. They concluded that there was not enough evidence to determine that IUI resulted in more live births or pregnancies than ICI.

Carroll and Palmer (2001) conducted a prospective randomized cross over control study on 62 single fertile women choosing to use donor sperm. They had a total of 189 cycles (94 IUI and 95 ICI). The resulting pregnancy rate was 15% and 9% respectively (p=0.04) which indicated that IUI was more effective than ICI. On the other hand, Hogerzeil et al. (1988) studied 53 women who either had at home ICI (n=29) or in clinic ICI (n=24). In the first 6 cycles 13 pregnancies resulted in the home ICI group while only 11 pregnancies resulted in the clinic group. Additionally, they followed 138 couples who did not meet the inclusion criteria. Of these 45 had opted for at home insemination and 20 of them ended up with a pregnancy.

In conclusion, there is a lot of room to learn more about the pregnancy rates of ICI and the experience of at-home artificial insemination. With 12% of women of child bearing age experiencing infertility there is an important contribution to be made to the fertility field. Using the Mosie Baby at-home artificial insemination kit is a low cost option that could potentially be a first line alternative for many people seeking to conceive. Therefore, it is important to understand the experience and pregnancy rates of people who have chosen to use the Mosie Kit to get pregnant at home. This study will provide valuable information for the fertility industry as a whole, as well as, will provide information for a follow up study where people choosing to use the Mosie Kit will be prospectively followed to capture their data in real time. Together these studies will provide a better understanding of at-home insemination success, safety and perception.

